## 16.5.4 Hepatic Assessment Flow Chart

#### **Hepatic Assessment Flow Chart**

#### 16.5.5 Factors to Consider in Assessing Potential DILI

When there is a potential DILI, it is important to thoroughly assess the patient's history, hepatic risk factors, clinical condition and hepatic function until resolution (normal or baseline levels).

Answers to the following questions should be recorded in source documents and in appropriate CRFs as outlined in the DEGs.

#### 16.5.5.1 Study Medication

Considerations should include the following: What was the time interval between administration of study medication and the laboratory abnormality(ies)? What is the status of study medication use: Continuing? Interrupted? Discontinued? Was the patient re-challenged with study medication?

#### 16.5.5.2 Treatment

Record any concomitant treatments.

#### 16.5.5.3 Signs and Symptoms (associated with the potential DILI event)

Does the patient have a concomitant illness? Does the patient currently exhibit signs or symptoms of hepatitis/DILI? What are the patient's signs and symptoms (see examples below)? What are the pertinent findings from medical history, physical/laboratory examination (e.g., fatigue, nausea, vomiting, right upper quadrant pain or tenderness, fever, rash, and/or eosinophilia > 5%, hepatomegaly, splenomegaly, etc.) that could suggest DILI?

Category	Examples of Signs and Symptoms

The information in this document is the property of OncoEthix and is confidential. Neither the document nor the information contained therein may be reproduced or disclosed outside OncoEthix without their written consent.

Blood/lymphatic	Eosinophilia, coagulopathy, susceptibility to
	bleeding/bruising
Circulatory	Varicose veins, edema
Constitutional	Fever, fatigue, malaise, weight gain, other (identify).
Digestive/hepatic	Anorexia, diarrhea, bloody or black stool, light-colored
	stools, nausea, vomiting, hematemesis, upper quadrant
	abdominal pain, upper quadrant tenderness, hepatomegaly,
	jaundice, splenomegaly, ascites, cholestasis
Endocrine/reproductive	Loss of libido
Integumentary	Rash, pruritus
Muscular	Myalgia
Nervous	Changes in mental status or level of consciousness
Urinary	Dark urine

# 16.5.5.4 Confounding Variables

What are the relevant medical history and findings? What is the differential diagnosis? What risk factors does the patient have for hepatic injury? (See examples below.) Provide onset of risk factor and duration.

Category	Examples of Confounding Variables
Subject medical history	Autoimmune disorder, cancer, Gilbert's syndrome, obesity, Wilson's
	disease
Substance use/abuse	Alcohol, illegal drugs, illegal intravenous (IV) drugs
Prior & Concomitant Medications:	History of recent concomitant acetaminophen (APAP)/paracetamol
Review all non-study medications	use, excessive nonsteroidal anti-inflammatory drug (NSAID) intake,
and therapies, including: over-the-	use of non-study drug or therapy that can cause liver damage or
counter (OTC), as well as	idiosyncratic adverse drug reactions
prescription. Ask the patient to bring	
products/packaging to site and	
review contents.	
Herbal and nutritional supplements	Herbal, complementary therapies, and nutritional supplements
Adulteration of products	History of previous exposure to the product or a similar product, and
	information on potential contamination or adulteration of products
Chemical exposure	Occupational or in other situations
Potential exposure to infectious	Infectious hepatitis, transfusion, travel, tattoos, sexually transmitted
agents	diseases, new sexual partner, shared needles
Special Diet	Special diet started since randomization
Other	Recent physical trauma, excessive exercise, or other prolonged
	physical exertion
Family history	Autoimmune disorder, cancer, Gilbert's syndrome, Wilson's disease

# 16.5.5.5 Evaluation algorithm for potential DILI if there are no other clinical reasons

Note: If clear etiology for the laboratory abnormalities has been confirmed, Stage 1 and 2 testing may not be required. In this case, consultation with the Sponsor is recommended.

#### Stage 1 work-up should be performed within 48-72 hours:

- ALT
- AST
- Bilirubin: total, direct, indirect
- Alkaline phosphatase (ALP)
- Prothrombin Time (PT)/international normalized ratio (INR)
- Creatine phosphokinase (CPK)
- Manual eosinophil count (if automated count was elevated)
- Toxicology screen for drugs of abuse (including ethanol) and for acetaminophen/paracetamol level should also be sent. Investigators may order additional toxicology tests as clinically indicated.
- Evaluate patient for the following signs and symptoms: fatigue, nausea, vomiting, right upper quadrant abdominal pain or tenderness, fever, rash.
- Obtain the following additional history and assessment for associated risk/confounding factors:
  - More detailed history of symptoms and prior or concurrent illness
  - Aminotransferase values obtained prior to the study or administration of study medication
  - Alcohol consumption (recent and historical)
  - Acetaminophen (APAP)/paracetamol use
  - New prescription, concomitant, or non-prescription (including herbal and other dietary supplements) medications
  - Unusual foods (e.g. mushrooms) or special diets. Consumption of seasonal foods.
  - Recreational drug use
  - Prior history of liver injury or disease, including but not limited to Gilbert's syndrome, autoimmune disorders, cancer, Wilson's disease, NASH, alcoholic or infectious hepatitis, biliary tract disease, hypoxic/ischemic hepatopathy
  - Obesity/abdominal adiposity (record weight, height, and waist circumference)
  - Occupational history and history of exposure to chemical agents or other environmental toxins
  - Recent travel (last three [3] years)
  - Transfusion history
- Perform the following required laboratory tests:
  - Albumin
  - Eosinophils (percentage and absolute; obtain manual count if automated count is elevated)
  - Viral hepatitis serologies (obtain appropriate consent prior to testing, if required locally)
    - A (IgG, IgM)
    - B (HepBs Ag, Hep Bs Ab, Hep Bc Ab, Hep Be Ag)
    - C (RNA)
    - D (requires concomitant hepatitis B infection)
  - Human Immunodeficiency Virus (HIV) testing (obtain appropriate consent prior to testing, if required locally)
  - Evaluation for autoimmune hepatitis:
    - Serum gamma globulin levels/ serum protein electrophoresis
    - Antinuclear antibody (ANA)
    - Anti-mitochondrial antibody (if ALP or TBL >ULN)
  - If AST/ALT ratio is greater than one (1) with suspicions of increased alcohol intake, perform the following:
    - Gamma-glutamyl transferase (GGT)
- Obtain a right upper quadrant ultrasound

The information in this document is the property of OncoEthix and is confidential. Neither the document nor the information contained therein may be reproduced or disclosed outside OncoEthix without their written consent.

# Stage 2 work-up tests should be drawn within one (1) week of receiving the Stage 1 work-up results and the results of Stage 1 evaluation are negative.

Note: A specific test may be performed earlier if the investigator determines that the clinical presentation leads to a certain diagnosis.

# Stage 2 work-up:

- Perform the following laboratory tests:
  - Genetic test for Gilbert's disease if there is a suspicious history. Ensure appropriate patient consent is obtained for this test.
  - Viral hepatitis E (IgG and IgM, obtain appropriate consent prior to testing, if required locally)
  - Anti-smooth muscle antibody
  - Anti-liver-kidney microsomal antibody
  - Anti-soluble liver antigen
  - Serologies for the following:
    - Cytomegalovirus (CMV) (IgG, IgM)
    - Epstein-Barr Virus (EBV) (IgG, IgM)
    - Herpes simplex
    - Toxoplasmosis
    - Varicella
    - Parvovirus
  - Ceruloplasmin
  - Serum alpha-1 anti-trypsin
  - Genetic test for hemochromatosis. Ensure appropriate patient consent is obtained for this test
  - Iron Studies:
- serum ferritin,
- serum iron,
- total iron binding capacity
- Consider referral to hepatologist/gastroenterologist
- Consider screen for celiac disease and cystic fibrosis if clinically indicated
- If laboratory tests or ultrasound evidence of biliary tract obstruction, consider obtaining Endoscopic Retrograde Cholangiopancreatography (ERCP) or Magnetic Resonance Cholangiopancreatography (MRCP)

If applicable, request copies of hospital discharge summaries, consultation reports, pathology reports, special studies (e.g. imaging or biopsy), etc.

16.5.5.6 Potential diagnosis

What diagnosis do the history, clinical course, and laboratory tests suggest?

16.5.5.7 Overall clinical impression

What are the investigator's overall clinical impressions (e.g., differential diagnosis, potential alternative causes)?

16.5.5.8 Treatment plan

What is the plan for treatment and follow-up?

1. INTRODUCTION

This SAP is a companion document to the protocol OTX015_108/MK-8628-003, *A Phase IB Trial with OTX015/MK-8628, a Small Molecule Inhibitor of the Bromodomain and Extra-Terminal (BET) Proteins, in Patients with Selected Advanced Solid Tumors*. In addition to the information presented in the protocol statistical considerations section which provides the principal features of analyses for this trial, this SAP provides additional statistical analysis details/data derivations and documents modifications or additions to the analysis plan that are not “principal” in nature and result from information that was not available at the time of protocol finalization.

2. ANALYTICAL AND METHODOLOGICAL DETAILS

2.1 Responsibility for Analyses/In-House Blinding

The statistical analyses of the data obtained from this study will be the responsibility of the Clinical Biostatistics department of the Sponsor.

The trial is open-label, i.e., subjects, Investigators, and Sponsor personnel will be aware of subject treatment assignment after each subject is enrolled and treatment is assigned. Allocation to treatment will not be randomized.

2.2 Statistical Design and Sample Size

The study is designed to assess the safety of OTX015/MK-8628 in patients with advanced or metastatic solid tumors. The small numbers per cohort are not intended for statistical hypotheses. Treatment decisions will be made by the SMC.

In study part 1, up to 48 patients evaluable for DLT were expected in QD Regimens 1 and 2 (i.e. up to 24 patients per regimen, 6 patients per four dose levels) depending on the number of patients experiencing DLTs.

In study part 2, up to 42 evaluable patients (6-14 per three dose levels) will be included in the BID regimen.

Overall, a total of up to 90 evaluable patients are expected to be accrued in this study. The final sample size will depend on the number of patients experiencing DLTs at each DL and in each regimen, and may be increased if the MTD is not reached and additional DLs are required.

2.3 Study Objectives

Primary Objective

- To determine the Maximal Tolerated Dose (MTD) defined as the recommended phase II dose for three distinct regimens of OTX015/MK-8628 administered orally to patients with selected advanced solid tumors.

Secondary Objectives

- To assess the safety profile of single-agent OTX015/MK-8628
- To characterize pharmacokinetics parameters and pharmacodynamics of OTX015/MK-8628
- To determine the antitumor activity of OTX015/MK-8628 in selected solid tumors

2.4 Study Endpoints

Primary Endpoint

- The number of patients experiencing at least one DLT in cycle 1 (day 1 to 21) for each of the regimens independently

Secondary Endpoints

- *Safety*: Incidence, severity and relationship of AEs, laboratory abnormalities, SAEs, discontinuations due to AEs, dose adaptations due to AEs, and DLT
- *Efficacy*: The number of patients with clinical benefit (defined as complete response, partial response or stable disease) and progressive disease based on the best overall response from tumor evaluations performed every 2 cycles, according to RECIST v1.1 or PCWG2, and tumor marker assessment
- *Pharmacokinetics*: Plasma parameters of OTX015/MK-8628 as appropriate and according to analyses performed (non-compartmental or nonlinear mixed effect modelling)
- *Pharmacodynamics*: Efficacy signal or incidence and severity of AEs along with PK parameters, analyzed in relation to the most pertinent biomarker(s), if any

2.5 Analysis Populations

Evaluable for DLT: Patients who receive at least 85% of the planned dose of study drug (18 days for QD Regimen 1 and the BID regimen, or 6 days for QD Regimen 2) or experience DLT during the first 21-day cycle

Treated population: Patients who receive at least one dose of study drug

Evaluable for efficacy: Patients who receive at least 2 complete cycles (6 weeks) of treatment and have undergone baseline assessment and one on-study tumor assessment, or who discontinue early due to disease progression

2.6 Statistical Methods

The study is designed to assess the safety of OTX015/MK-8628 in patients with solid tumors. The small numbers per cohort are not intended for statistical hypotheses.

Quantitative variables will be summarized using descriptive statistics; continuous variables will be presented as N, mean and/or median, standard deviation, range, and categorical variables will be presented using frequencies and percentage. For CRPC patients, since no response was observed, waterfall plots will not be prepared.

Patient disposition and demographics will be analyzed in all included patients, response will be analyzed in patients evaluable for efficacy, and safety will be analyzed in the treated population with an additional analysis in patients evaluable for DLT.

AEs will be coded according to the most recent version of the Medical Dictionary for Regulatory Activities (MedDRA) and will be tabulated by System Organ Class and Preferred Term. Laboratory values outside normal limits will be summarized using the NCI-CTCAE version 4.03. Concomitant medications will be coded according to the WHO Drug Dictionary.

Data will be presented by dose level, regimen, and where appropriate by indication. No imputations for missing data will be made.

Pharmacokinetics and pharmacodynamics will be analyzed and reported separately.

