#### 9.2.1 PSA

# For control/relief/eliminate end points

The PCWG2 advises against reporting PSA response rates because they are of little value given the uncertain significance of a defined degree of decline from baseline, be it 50% or 30%, and no criterion has been shown prospectively to be a surrogate of clinical benefit (Fleming et al., 2006).

To report PSA-based outcomes, PCWG2 recommends that the percentage of change in PSA from baseline to 12 weeks (or earlier for those who discontinue therapy), as well as the maximum decline in PSA that occurs at any point after treatment be reported for each patient using a waterfall plot (Seidman et al., 1992). Waterfall plots provide a broader and more sensitive display of data, and are more informative until a validated surrogate of clinical benefit becomes available. PCWG2 recommends that the same waterfall plot be used to illustrate outcomes for noncytotoxic agents. It discourages the use of changes in PSA-doubling time or PSA slope as a primary end point, given that their clinical significance is uncertain, and also recommends avoiding reporting duration of PSA control, as described in PCWG1 guidelines, because its interpretation varies between investigators.

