#### For prevent/delay end points

Progressing disease on bone scan is considered when a minimum of two new lesions is observed. PCWG1 made the provision that a worsening bone scan on the first follow-up manifests tumor "flare"; PCWG2 does not recommend performing a follow-up bone scan before 12 weeks of treatment unless clinically indicated. At the first 12-week reassessment, defining disease progression requires a confirmatory scan (which shows additional new lesions compared with the first follow-up scan) performed 6 or more weeks later, because lesions visible at the 12-week assessment may represent disease that was not detected on the pretreatment scan. When further progression is documented on the confirmatory scan, the date of progression recorded for the trial, is the date of the first scan that shows the change.

Note that symptoms will not be evaluated in this phase Ib study.

Table 16: The Prostate Cancer Clinical Trials Working Group (PCWG2) Response Criteria

Variable	PCWG2 Criteria (Scher et al., 2008)
PSA	For control/relieve/eliminate end points:
	Record the percent change from baseline (rise or fall) at 12 weeks, and separately, the
	maximal change (rise or fall) at any time using a waterfall plot
	Progression:
	Decline from baseline : record time from start of therapy to first PSA increase that is $\geq$
	25% and $\geq$ 2 ng/mL above the nadir, and which is confirmed by a second value 3 or
	more weeks later (i.e., a confirmed rising trend)
	The requirement of an increase of 5 ng/mL is decreased to 2 ng/mL, and the
	requirement for a 50% increase is reduced to 25%
	Recording the duration of PSA decline of little value
	No decline from baseline:
	PSA progression $\geq 25\%$ and $\geq 2$ ng/mL after 12 weeks
Soft-tissue	For control/relieve/eliminate end points:
lesions	
	Use RECIST with caveats
	Only report changes in lymph nodes that were $\geq 2$ cm in diameter at baseline
	Record changes in nodal and visceral soft tissue sites separately
	Record complete elimination of disease at any site separately
	Confirm favorable change with second scan
	Record changes using waterfall plot
	For delay/prevent end points:
	Use RECIST criteria for progression, with additional requirement that progression at
	first assessment be confirmed by a second scan 6 or more weeks later
D	Note that for some treatments, a lesion may increase in size before it decreases
Bone	For control/relieve eliminate end points:

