#### 11.4 Statistical Methods

Quantitative variables will be summarized using descriptive statistics; continuous variables will be presented as N, mean and/or median, standard deviation, range, and categorical variables will be presented using frequencies and percentage. For CRPC patients, waterfall plots for percent change from baseline at 12 weeks, as well as maximal change at any time will be prepared.

Patient disposition and demographics will be analyzed in all included patients, safety will be analyzed in the treated population with an additional analysis in patients evaluable for DLT for the dose escalation part, and response will be analyzed in patients evaluable for efficacy.

AEs will be coded according to the most recent version of the Medical Dictionary for Regulatory Activities (MedDRA) and will be tabulated by System Organ Class and Preferred Term. Laboratory values outside normal limits will be summarized using the NCI-CTCAE version 4.03. Concomitant medications will be coded according to the WHO Drug Dictionary.

Data will be presented by dose level and regimen for the dose escalation part, by indication and/or regimen for the dose expansion part of the study. No imputations for missing data will be made.

A Statistical Analytical Plan (SAP) will be finalized prior to analysis. Any deviations from the statistical methods in the study protocol will be described and justified in the SAP and in the statistical report.

Pharmacokinetics will be analyzed and reported separately, as described in Section 10.

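### SAP 2.6 withdraws the two planned CRPC waterfall plots only because no response was seen, a reason that does not fit a per-patient display of rises and falls

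*SAP*

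**What the plan says.** Protocol 11.4 commits to the displays outright: "For CRPC patients, waterfall plots for percent change from baseline at 12 weeks, as well as maximal change at any time will be prepared". It also sets a standard for later changes: "Any deviations from the statistical methods in the study protocol will be described and justified in the SAP and in the statistical report".

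The PSA row of Table 16 (protocol 9.2) describes the matching quantities. The first is "Record the percent change from baseline (rise or fall) at 12 weeks"; the second, recorded separately, is the "maximal change (rise or fall) at any time using a waterfall plot". Protocol 9.2.1 gives the rationale: "The PCWG2 advises against reporting PSA response rates because they are of little value". It recommends per-patient waterfall plots as the way to report PSA outcomes.

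SAP 2.6 then states: "For CRPC patients, since no response was observed, waterfall plots will not be prepared". It gives no other reason and does not say whether the response meant is PSA response or tumor response. SAP 2.4 keeps tumor marker assessment in the efficacy endpoint.

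**The concern.** A display planned without condition is cancelled on the strength of the result it would have shown. In an open-label trial the team sees outcomes as they accrue, so an output dropped for this kind of reason is an outcome-dependent omission, even when it is openly declared.

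The stated reason would make sense for a table of responders. It does not make sense for a plot in which every patient has a bar and a rise counts as much as a fall. What is at stake is the patient-by-patient view of PSA: whether any CRPC patients had falls short of a response, and how large the rises were in the others. The statement that no response was observed carries neither piece of information.

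**Working it through.** No power, alpha or event count enters this point. The check is a comparison of texts, with a little counting.

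1. **What was planned.** Protocol 11.4 names two CRPC displays (12-week change; maximal change at any time). Neither depends on a patient having responded.

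2. **What remains.** SAP 2.6 withdraws waterfall plots for CRPC patients as a whole, so 2 − 2 = 0 of the named displays are kept.

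3. **Which variable is plotted.** Section 11.4 does not name PSA. The link is by wording: its pair of quantities, 12-week change and maximal change at any time, is the pair in the PSA row of Table 16. The soft-tissue row of that table also asks for a waterfall plot, but mentions neither the 12-week value nor the any-time maximum.

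4. **Does the display need responders?** For each patient the bar is 100 × (PSA on study − baseline PSA) / baseline PSA. It exists for anyone with a baseline value and the relevant later value. No response threshold appears in the formula, and Table 16 admits both signs. With zero responders the plot has the same number of bars as with several.

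5. **Does the reason fit if response means tumor response?** No. Table 16 asks for soft-tissue changes to be shown in a waterfall plot too, and protocol 9.1 has any tumor shrinkage reported even when it falls short of the RECIST response criteria.

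6. **Are the data there?** Protocol 7.2 schedules tumor markers on day 1 of every cycle, and section 9 names PSA as the CRPC marker. Day 1 of cycle 5 falls 4 × 21 = 84 days, or 12 weeks, after first dose when no cycle is delayed.

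7. **Which version governs?** The supplied protocol has two regimens and 48 + 50 = 98 evaluable patients, with 10 CRPC patients among the 50 in expansion. The SAP has three regimens and 48 + 42 = 90, with a BID part and no expansion cohorts. The SAP therefore seems to rest on a later protocol that was not supplied, and neither document says how many CRPC patients were treated.

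8. **A loose end in the definition.** Protocol 9.2.1 speaks of "the maximum decline in PSA that occurs at any point after treatment", a fall only, whereas Table 16 allows a rise or a fall. Section 11.4 says maximal change, which is closer to Table 16. Any restored display has to settle this.

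**The case against.** The strongest defence is that the SAP did what it should. Protocol 11.4 allows deviations that are described and justified in the SAP. The SAP introduction says that it records changes that are not principal and that arise from information unavailable when the protocol was finalized. Dropping a descriptive figure, in plain words, falls within that scope. The synopsis does not mention the plots at all. SAP 2.6 still summarizes continuous variables by N, mean or median, standard deviation and range, by indication where appropriate; applied to PSA change, the range would show the largest fall and the largest rise.

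Most of this stands. It establishes disclosure and small impact. It does not make the reason fit: 11.4 asks for a justification, and the absence of responders does not justify omitting a display that 9.2.1 recommends in place of response rates. Two better reasons may exist, an amended protocol or too few CRPC patients, but the SAP gives neither.

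Three stronger readings are tempting, and the documents do not support them.

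- A reader might infer that an unfavorable result is being hidden. The SAP states the negative result in the same sentence.
- A reader might infer that no per-patient PSA output will exist. The SAP itemizes no listings or figures for any endpoint, so its silence on a PSA listing proves little.
- A reader might want to say how high a response rate remains compatible with none observed. The number of CRPC patients is not given, so any such limit would rest on an assumed denominator, and it would not bear on whether the reason fits the display.

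**Conclusion.** The point holds as a minor one, for consideration. Both CRPC waterfall plots in the supplied protocol 11.4 are withdrawn for a reason that depends on the outcome and does not apply to a per-patient plot of rises and falls. The loss is the bar-by-bar PSA view in one tumor type. PSA collection, the tumor marker endpoint and group summaries are not withdrawn, and DLT and MTD conclusions are unaffected.

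The conclusion rests on two assumptions. The first is that 11.4 refers to PSA, which its wording supports but does not state; the reason fails for soft-tissue change as well. The second is that the protocol version governing the SAP still planned the plots. The SAP's having to withdraw them suggests so, but the text is not available. A reader might call this a breach of the protocol. That goes too far, because the deviation is declared and only its justification is weak.

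**What to change.** Replace the clause in SAP 2.6 with text along these lines:

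> For CRPC patients with a baseline PSA and at least one later PSA, the 12-week percent change from baseline (or the change at the last on-treatment PSA, for patients with no 12-week value because treatment ended) and the largest rise or fall at any time, as defined in Table 16, will be shown for each patient regardless of response. Waterfall plots will be used, or a per-patient listing if CRPC numbers are very small.

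State in the SAP and in the report that this text was written after response results were known. If a later protocol version withdrew the plots, or the number of CRPC patients is too small to plot, cite that reason in place of the observed result.

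The cost is a short SAP revision and two figures or one listing, from PSA values already scheduled for collection. No new data are needed.
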